## 13 Exploratory Analyses

### 13.1 Associations Between the Pulmonary and Pulmonary+ Outcomes and Time to Sustained Recovery

At the early futility assessment when 300 participants (150 per study arm) are enrolled and have Day 5 data, estimated treatment differences in the pulmonary and pulmonary+ ordinal outcomes on Day 5 are used to identify promising investigational agents to continue to be studied with the clinical outcome of “time to sustained recovery”. In exploratory analyses, we will investigate whether the early pulmonary and pulmonary+ outcomes on Day 5 are an adequate predictor for time to sustained recovery, to re-evaluate our initial futility decision rule.

- Associations between the pulmonary and pulmonary+ ordinal outcomes at Day 5 with time to sustained recovery will be estimated using Cox proportional hazards models, pooled across treatment groups. To illustrate these associations, median time to sustained recovery will be estimated by category of the ordinal outcomes on Day 5, using Aalen-Johansen estimates of the cumulative incidence function.

Ideally, the goal would be to evaluate the extent to which treatment differences in the pulmonary outcomes on Day 5 predict treatment differences in time to sustained recovery through Day 90. A detailed analysis plan will be developed at a later time.

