For time-to-event analyses, if strata are too small for fitting separate baseline hazard functions, strata may be added as a categorical covariate to models instead. Whenever possible, however, analyses should be stratified by disease severity (with separate baseline hazard functions).

For **binary outcomes**, probabilities will be compared between the investigational agent and its control group using Cochran-Mantel-Haenszel tests (CMH) or logistic regression. If the numbers are sufficiently large, CMH tests will be stratified according to the planned randomization strata (disease severity and site pharmacy), as described above under “stratification”. Odds ratios (OR) with 2-sided 95% confidence intervals (CI) will be estimated using logistic regression models.

For longitudinally measured binary outcomes, the treatment effect through follow-up will be estimated with 95% confidence intervals using generalized estimating equations (GEE) with a logit link function; the treatment effect is estimated via the interaction between the indicator for treatment group and the indicator for follow-up (versus baseline) visits. When there is more than one follow-up visit, “visit number” (day) may be included as categorical variable in the model, for variance reduction; alternatively, “time” may be included as a continuous variable.

**Ordered categorical outcomes (pulmonary and pulmonary+)** will be compared between treatment groups using proportional odds models, and the summary OR will be estimated with a 2-sided 95% CI. Additionally, to aid the interpretation, the ordinal outcome will be dichotomized according to cumulative probabilities of the ordered categories, comparing treatment groups for proportions of participants in category 1, in the “best 2 categories”, “best 3 categories”, etc.; these comparisons will be performed using logistic regression (or stratified CMH tests).

For interim analyses of the ordinal outcomes, if one or more recently enrolled participants have died (i.e., their outcome status is known) but their current administrative follow-up has not yet reached the time point at which the treatment groups are to be compared (e.g., day 5), analyses will be restricted to participants with administrative follow-up greater or equal to the target time point.

Models will be adjusted for the baseline categories of the pulmonary+ outcome and for study pharmacy, by including the corresponding indicator variables in the model.

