The DSMB will be asked to review whether the discordance is attributable to a positive or negative effect on extra-pulmonary organ dysfunction (the difference in the two ordinal scale categories, the conditions included in pulmonary+ but not in the pulmonary endpoint), and whether the same ordinal outcomes assessed on other days yield similar results, and weigh the risk/benefit profile. For example, if there is a significant positive effect on the pulmonary score and the lack of significant effect on the pulmonary+ score is driven by a lack of difference in the milder thrombotic symptoms in category 4 of the pulmonary+ scale (e.g. deep venous thrombosis) and there is no evidence of any raised risk of thrombosis overall, the agent will advance. Conversely, if the agent is superior to the control group with respect to the pulmonary outcome, but clearly inferior to the control group with respect to the pulmonary+ outcome or has a concerning safety profile, it will not advance.

Analyses of the primary efficacy endpoint, time to sustained recovery, will also be provided to the DSMB, as supporting information. These analyses are described in section [8.1](#).

If available, subgroup analyses by nAb status at study entry (nAb negative or positive) will also be provided.

### 10.2.2 Analyses of the Pulmonary and Pulmonary+ outcomes on Day 5

- Treatment groups will be compared by intention to treat.
- For each of the two ordinal outcomes, the number and percentage of participants in each of the categories on Day 5 will be tabulated, and the OR of the active versus control group will be estimated using a proportional odds model with indicators for the investigational agent group (active versus control) and for the categories of the ordinal pulmonary+ outcome at baseline (to adjust for baseline severity of illness). The model will be stratified by site pharmacy.

The summary tables will show the adjusted summary OR with 95% CI, estimated as described above, as primary analysis. In addition, the unadjusted summary OR with 95% CI will be shown as sensitivity analysis (estimated using a proportional odds model without adjustment for the pulmonary+ baseline category or site pharmacy). In the case that the adjusted OR differs substantially from the unadjusted OR, the reason for the deviation will be explored.

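### SAP 13.1 judges Day 5 status as a predictor of sustained recovery without a baseline severity term, so the association can partly or wholly reflect severity at entry

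*SAP*

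**What the plan says.** SAP 13.1 sits under Exploratory Analyses. Its purpose is to see whether the Day 5 ordinal outcomes are "an adequate predictor for time to sustained recovery, to re-evaluate our initial futility decision rule". Two pieces of work are specified: associations of Day 5 category with "time to sustained recovery will be estimated using Cox proportional hazards models, pooled across treatment groups", and median time to recovery by Day 5 category from Aalen-Johansen estimates. No baseline covariate and no criterion for adequacy are given. The section then adds: "Ideally, the goal would be to evaluate the extent to which treatment differences in the pulmonary outcomes on Day 5 predict treatment differences" on the primary endpoint. It closes with "A detailed analysis plan will be developed at a later time".

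The futility test is built differently. SAP 10.2.2 fits a proportional odds model with treatment and baseline pulmonary+ category, the latter "to adjust for baseline severity of illness", stratified by site pharmacy. The unadjusted odds ratio is only a sensitivity analysis.

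**The concern.** A check meant to inform a baseline-adjusted rule should condition on the variable that the rule conditions on. Participants on more oxygen at entry tend to be on more oxygen at Day 5 and to go home later. A pooled model without a baseline term credits all of that to Day 5. Treatment cannot change severity at entry, so that part of the association does not bear on whether a Day 5 treatment effect carries through to recovery.

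What is at stake is the later re-evaluation of a go/no-go step that successive agents in the platform pass through. A raw association is close to foreseeable and would say little about whether that step is well chosen.

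**Working it through.** **1. Does a general rule supply the missing covariate?**
- SAP section 3 states "Models will be adjusted for the baseline categories of the pulmonary+ outcome and for study pharmacy", but under the ordered categorical outcomes, where the models are proportional odds comparisons of the arms. It is not written for a Cox model with Day 5 category as the predictor.
- Section 3 also prefers time-to-event analyses stratified by disease severity, but defines that term as randomization strata 1 and 2, not oxygen category. Appendix E-5 reports that nobody was randomized in stratum 2 for AZD7442, so in that trial this stratification adjusts for nothing.
- Section 10.2.2 notes that, within stratum 1, baseline pulmonary+ category is simply oxygen requirement (categories 2, 3 and 4). This is the variation that the stratum definition misses.

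No rule fills the gap.

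**2. Do the documents support the two links?** Baseline to Day 5: the risk score in section 13.2 uses baseline pulmonary category to predict Day 5 category 5-7. Baseline to recovery: section 9.2 reports that nAb-negative participants were sicker at entry and less likely to reach sustained recovery. The second link is indirect. Neither is quantified.

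**3. The plan's own figures.** Section 13.1 states none. Two related figures were reproduced.
- Futility test (section 1.4: N=300, OR 1.60, one-sided 0.30, power 95%). Whitehead: N = 12(z0.70 + z0.95)² / [ln(1.6)² (1 − Σp̄³)] = 12(0.524 + 1.645)² / [0.2209 (1 − Σp̄³)] = 255.6 / (1 − Σp̄³). The control distribution is not given. Four assumed seven-category distributions, with 1 − Σp̄³ of 0.978, 0.931, 0.845 and 0.738, give power 0.964, 0.959, 0.949 and 0.932 at N=300, all within 2 points of 95%.
- Event target (RRR 1.25, 90% power, one-sided 0.025). Schoenfeld: 4(1.960 + 1.282)² / ln(1.25)² = 844.1, so 845 against the stated 843. Power at 843 events is 0.8996.

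Both stand. Neither depends on section 13.1.

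**4. Simulation in which Day 5 adds nothing beyond baseline.** All strengths are assumptions.
- Three baseline categories at 30/40/30%.
- Day 5 category (five levels among survivors) from baseline plus independent logistic noise, with log-odds of 0.5 to 1.5 per baseline category.
- Recovery time = 14 days + exponential with rate 0.035 × exp(−h × centred baseline category), h = 0.25 or 0.5. Day 14 is the earliest possible recovery (section 8.1). Censoring at Day 90, no deaths, no treatment effect.
- Cox model with Day 5 as a linear score, without and with two baseline indicators. Two-sided 5% test, 1,000 runs per setting.

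| Log-odds, baseline to Day 5 | h | Unadjusted HR per Day 5 category | Unadjusted significant, N=300 | Unadjusted significant, N=1,000 | Adjusted significant, N=300 / 1,000 |
|---|---|---|---|---|---|
| 0.5 | 0.25 | 0.97 | 10.8% | 22.4% | 4.8% / 4.8% |
| 1.0 | 0.25 | 0.94-0.95 | 23.2% | 60.1% | 5.2% / 5.4% |
| 1.0 | 0.50 | 0.90 | 65.8% | 99.2% | 4.5% / 4.5% |
| 1.5 | 0.50 | 0.87 | 90.4% | 100% | 5.4% / 4.8% |

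Adjusted hazard ratios are 1.00 throughout. The Monte Carlo standard error of a 5% rate is √(0.05 × 0.95 / 1,000) = 0.7 points.

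**5. Is baseline adjustment enough?** In a further scenario, an unmeasured factor drives both Day 5 and recovery. Treatment shifts Day 5 (conditional OR 1.6) but has no effect on recovery (treatment HR 1.00). The baseline-adjusted Day 5 association has HR 0.85 and is significant in 93.2% of 500 runs at N=300 and in 100% at N=1,000. A longer repeat at N=300 (4,000 runs) gave about 91%, with or without treatment in the model. Adjustment is therefore necessary but not sufficient.

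**The case against.** The strongest reply has four parts.

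- **The covariates are unspecified rather than excluded.** The section is exploratory and ends by deferring a detailed plan, which could name them. That is fair. But the deferral follows the sentence on treatment differences, and nothing commits it to changing the Cox model, which is the only model specified now.
- **A raw association is a legitimate answer to a prediction question.** This stands as far as it goes, and is a reason to keep the unadjusted results as description. The stated use, however, is to reconsider a rule that conditions on baseline, and for that the relevant quantity is what Day 5 adds.
- **The simulated null is extreme.** Those who die by Day 5 cannot recover, and those on invasive ventilation must still be discharged and spend 14 days at home, so some true association is built in. Agreed. The simulation shows how much association can arise from baseline alone, not that Day 5 is uninformative. It also scores significance, which 13.1 does not use as a criterion.
- **The fix does not establish surrogacy.** Correct, as step 5 shows.

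A reader might go further and infer that 13.1 would validate the futility outcome, or that agents could be wrongly stopped or advanced because of it. The documents support neither. Section 13.1 sets no pass criterion and itself names the treatment-difference question as the ideal. No agent's fate is decided there. The futility test is baseline-adjusted, section 10.2.1 frames the rule as a guideline within a broad assessment of the data, and the DSMB also sees the sustained recovery analyses at that look.

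**Conclusion.** The point holds as a gap in an exploratory analysis. Run as written, the 13.1 Cox model mixes Day 5 information with entry severity, and no general rule in the SAP prevents this.

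The size depends on strengths that the documents do not give. Under the assumed range, with Day 5 adding nothing beyond baseline, the unadjusted association is significant in about 11-90% of trials at N=300 and 22-100% at N=1,000, with hazard ratios of 0.97 to 0.87 per category, against about 5% after adjustment. The simulation leaves out deaths and has 91-93% recovered by Day 90, above the 84.3% implied by 843/1,000, so the figures illustrate the mechanism and do not forecast this trial.

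The futility decision, its error rates and the primary analysis are unaffected. Only the later re-evaluation of the rule is touched.

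**What to change.** In SAP 13.1:

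1. Include baseline pulmonary+ category (indicators or strata, as in 10.2.2) and treatment group in the Cox model for each Day 5 outcome.
2. Report the added predictive value of Day 5 over baseline, for example the likelihood-ratio statistic and the change in concordance when Day 5 is added. Keep the unadjusted association and the medians by Day 5 category as descriptive results.
3. State that the individual-level association, even adjusted, does not by itself support the futility rule, and that this needs the treatment-difference analysis the section calls ideal. Write that deferred plan before the results are used to re-evaluate the rule.

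Medians by Day 5 category within baseline category are optional, where cell sizes allow; at N=300 many cells would be sparse.

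The cost is two or three sentences. The covariate is already collected at entry and already used in the futility model. The reported Day 5 association will probably look weaker.

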### 13.2 Disease Progression Risk Score

A disease progression risk score, calculated at baseline, will be used to form subgroups of participants with low or high predicted risk for subgroup analyses for safety and efficacy outcomes, and to pair participants for the win ratio analyses described in section 8.2.

The risk score for a participant is defined as the estimated *probability that the Pulmonary outcome on Day 5 is in one of the categories 5, 6 or 7* (5=non-invasive ventilation or high-flow oxygen, 6=invasive ventilation, 7=death). The probability is estimated using a logistic regression model for the corresponding binary outcome (Pulmonary categories  $\geq 5$  vs  $< 5$  on Day 5) with the following baseline predictors: age, sex, Pulmonary category at baseline, days since symptom onset, NEW score, and indicator variables for the following risk factors: asthma/COPD, diabetes, CVD, heart failure, hypertension, HIV or other immune deficiency, and renal impairment. The risk score will be derived from the pooled data for the investigational agent/placebo groups. Thus, the risk score will be specific to each investigational agent.

## 14 Unblinding of Treatment Comparisons

For any investigational agent, trial results will be unblinded when the pre-specified number of primary endpoints is reached; results may be unblinded earlier upon the recommendation of the DSMB if the sponsor and study leadership concur. In this case, trial results for the investigational agent will be unblinded and reported with available data through 90 days of follow-up. After that, data collection will continue as outlined in the data collection plan; under protocol version 3.0, death and re-hospitalizations will be recorded through 18 months.

While the trial is ongoing, access to any data summaries by treatment group (investigational agent or control groups) will be restricted to the members of the DSMB, the DSMB's Executive Secretary, and the unblinded statisticians.

When the trial for an investigational agent is concluded, data for the investigational agent and the corresponding pooled control group will be unblinded and provided to the study team.

The timing of the unblinding of data for one agent may require consideration, if:

- the control group is substantially shared with another agent for which the trial is still ongoing, **and**
- pooled data on treatment outcomes for the ongoing trial are available to investigators.

In this case, the need for a speedy unblinding has to be balanced with maintaining trial integrity for other agents in the platform trial, and the DSMB will be consulted as to the timing of the unblinding.

## 15 Distribution of Reports

- Open report: ACTIV-3 leadership team; DAIDS Medical Officer; selected NIAID staff; representatives of the companies; and all recipients of the unblinded closed report. After the DSMB meeting, the open report and the DSMB summary statement will be posted to the trial's web site, open to all investigators.
- Closed report: DSMB members, Executive Secretary of the DSMB, unblinded statisticians.
- Web reports (accessible by all investigators and study staff):
  - Enrollment summaries by site and over time (updated daily)
  - Baseline characteristics
  - Selected summary measures on data quality and study conduct (pooled across treatment groups).
- Additionally, selected summary measures on study conduct will be provided to study leadership upon request (pooled across treatment groups).

## Appendix A. Definition of the Pulmonary and Pulmonary+ ordered categorical outcomes

The Pulmonary categorical outcome is primarily defined based on oxygen requirements. The categories of the Pulmonary+ outcome are similar, except that categories 4 and 5 also capture selected extra-pulmonary complications, highlighted in red below.

Pulmonary outcome	Pulmonary+ outcome
1. Can independently undertake usual activities with minimal or no symptoms	1. Can independently undertake usual activities with minimal or no symptoms
2. Symptomatic and currently unable to independently undertake usual activities but no need of supplemental oxygen (or not above premorbid requirements)	2. Symptomatic and currently unable to independently undertake usual activities but no need of supplemental oxygen (or not above premorbid requirements)
3. Supplemental oxygen (<4 liters/min, or <4 liters/min above premorbid requirements)	3. Supplemental oxygen (<4 liters/min, or <4 liters/min above premorbid requirements)
4. Supplemental oxygen ( $\geq 4$ liters/min, or $\geq 4$ liters/min above premorbid requirements, but not high-flow oxygen)	4. Supplemental oxygen ( $\geq 4$ liters/min, or $\geq 4$ liters/min above premorbid requirements, but not high-flow oxygen) or any of the following: stroke (NIH Stroke Scale [NIHSS] <math>\leq 14</math>), meningitis, encephalitis, myelitis, myocardial infarction, myocarditis, pericarditis, new onset CHF NYHA class III or IV or worsening to class III or IV, arterial or deep venous thromboembolic events
5. Non-invasive ventilation or high-flow oxygen	5. Non-invasive ventilation or high-flow oxygen, or signs and symptoms of an acute stroke (NIHSS >14)
6. Invasive ventilation, extracorporeal membrane oxygenation (ECMO), mechanical circulatory support, or new receipt of renal replacement therapy	6. Invasive ventilation, ECMO, mechanical circulatory support, new receipt of renal replacement therapy, or vasopressor therapy
7. Death	7. Death

The term “usual activities”, in categories 1 and 2 for both outcomes, refers to activities of daily living that the participant was able to undertake prior to the current illness.

## Appendix B. Definition of Clinical Organ Failure and Serious Infection

According to the protocol, section 4.2.2., *clinical organ failure* is defined by development of any one or more of the following clinical events (see PIM for criteria for what constitutes each of these conditions):

- a. Respiratory dysfunction:
  - 1. Respiratory failure defined as receipt of high flow nasal oxygen, non-invasive ventilation, invasive mechanical ventilation, or ECMO
- b. Cardiac and vascular dysfunction:
  - 1. Myocardial infarction (MI)
  - 2. Myocarditis or pericarditis
  - 3. Congestive heart failure (CHF): new onset NYHA class III or IV, or worsening to class III or IV
  - 4. Hypotension requiring institution of vasopressor therapy
- c. Renal dysfunction:
  - 1. New requirement for renal replacement therapy
- d. Hepatic dysfunction:
  - 1. Hepatic decompensation
- e. Neurological dysfunction
  - 1. Acute delirium
  - 2. Cerebrovascular event (stroke, cerebrovascular accident [CVA])
  - 3. Transient ischemic events (i.e., CVA symptomatology resolving <24 hrs)
  - 4. Encephalitis, meningitis or myelitis
- f. Haematological dysfunction:
  - 1. Disseminated intravascular coagulation
  - 2. New arterial or venous thromboembolic events, including pulmonary embolism and deep vein thrombosis
  - 3. Major bleeding events (>2 units of blood within 24 hours, bleeding at a critical site [intracranial, intraspinal, intraocular, pericardial, intraarticular, intramuscular with compartment syndrome, or retroperitoneal], or fatal bleeding).

*Serious infection* is defined as:

- g. Serious infection:
  - 1. Intercurrent, at least probable, documented serious disease caused by an infection *other than* SARS-CoV-2, requiring antimicrobial administration and care within an acute-care hospital.

## Appendix C. Safety Data Collection

**Table C-1. Overview of Safety Data Collection** (protocol version 3, section 10).\*

	Infusion +2 hrs	Days 0-7	Day 14	Day 28	Day 90	Months 6, 12, and 18
Infusion-related reactions and symptoms	X					
Clinical AEs of any grade severity		X	X	X		
Grade 3 and 4 clinical AEs from Day 7 through Day 28 			X	X		
Targeted laboratory abnormalities of any grade		X (Day 5)				
Hospital admissions and deaths		Collected through Month 18				
Targeted clinical events collected as study endpoints 	Collected through Day 90					
SAEs not exempt from reporting (i.e., not considered a protocol specified exempt event) 	Collected through Day 90					
Any SAE related to study intervention	Collected through Day 90					
Unanticipated problems	Collected through Day 90					

 Grade 3 and 4 clinical AEs on Days 1-7 are reported each day; those occurring between Days 8 and 14 are reported at the Day 14 visit, and those occurring between Days 15 and 28 are reported at the Day 28 visit.

 Protocol-specified exempt serious events (PSEE); these events are listed below. See section 10.2.5 of the TICO study protocol and the PIM for information on PSEE.

\* In protocol version 2.0, the data collection is identical, except that hospital re-admissions and deaths are collected through Month 12 only.

